### 7.2.2. Data Handling Rules

In case a laboratory test result is *censored* (no numeric value is available, but only a verbatim term) then a numeric value will be imputed:

- For integer  $x$ :
  - If the value is  $<x$  then impute with  $x-1$ .
  - If the value is  $>x$  then impute with  $x+1$ .
- For mantissa (decimal part)  $x$ :
  - If the value is  $<y.x$  then impute with  $y.x-0.1$  (if  $x$  has 1 decimal place of precision).
  - If the value is  $>y.x$  then impute with  $y.x+0.1$  (if  $x$  has 1 decimal place of precision).

**Remark:** The value added or subtracted from the mantissa should follow from its mantissa.

**Example:**

If value is <5 or >10 impute with 4 and 11 respectively.  
If value is <5.3 or >10.7 then impute with 5.2 and 10.8 respectively.  
If value is <5.32 or >10.73 then impute with 5.31 and 10.74 respectively.

**7.2.3. Analysis Methods**

Laboratory abnormalities will be determined in accordance with the toxicity grading tables (Attachments 3), and in accordance with the normal ranges of the clinical laboratory. The worst abnormalities following vaccination will be summarized (ie, showing number and percentage) by regimen and presented per period/phase, with special attention to Grade 3 toxicities. Focus will be on clinical abnormalities that occur during Post-dose 1 and Post-dose 2 periods, as well as the Regimen Phase. Similar tables for worst abnormalities will be provided pooled by vaccine (dose). A listing will also be provided for subjects with any abnormal laboratory findings following vaccination.

**7.3. Vital Signs and Physical Examination Findings**

Vital sign abnormalities will be determined in accordance with the DMID Vital Signs Toxicity Grading (Attachment 3). Because vital signs are only assessed at screening and pre-vaccination (ie, pre-prime and pre-boost), descriptive statistics will not be generated for them. Instead, a listing will be generated for subjects with any abnormality.

It is important to note that a full physical examination was only conducted at screening. At other visits, only abbreviated, symptom-directed examinations are performed per the investigator's discretion. Therefore, only a listing of subjects with worst physical examination findings (ie, abnormalities) following vaccination will be provided.

Also, any clinically relevant vital signs or physical examination abnormalities occurring from signing of the ICF onwards until 42-day post-boost vaccination was recorded on the AE page of the eCRF and will be analyzed as AE.

**7.4. Electrocardiogram**

Note that a single, 12-lead ECG was performed at screening, pre-boost and 7 days post-boost, and interpreted locally. Additional ECG monitoring could be done at other time points during the study, only if clinically indicated based on signs and symptoms. Therefore, only a listing of subjects with an electrocardiogram abnormality following vaccination will be generated.

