study under Amendment 4, the sponsor offered a late boost vaccination to those subjects who did not receive it yet, unless participants had withdrawn from the trial or were not eligible to receive the boost. Vaccinated subjects have been following the same post-boost vaccination schedule as those subjects unaffected by the pause. Subjects who did not receive the late boost were encouraged to return for the 1-year post-prime visit. After restart of the study in the UK under Amendment 4, screening for Groups 1 and 2 restarted, but randomization to Group 3 was stopped to focus on the schedules for which an indication will be sought. After approval of Amendment 5, enrollment in the entire study will be stopped.

Subjects in the UK and France who reach the Day 365 visit prior to unblinding will be approached to consent for enrollment into the VAC52150 Vaccine Development Roll-over study (VAC52150EBL4001) for long-term surveillance (for a total of up to 60 months after the prime vaccination). After unblinding, only subjects who received Ad26.ZEBOV and/or MVA-BN-Filo will remain in the VAC52150 Vaccine Development Roll-over study for long-term surveillance. After unblinding, subjects who received placebo and have already been enrolled into the VAC52150 Vaccine Development Roll-over study will be discontinued from further participation in the roll-over study. The parent(s)/legal guardian of children born to vaccinated female subjects who became pregnant with estimated conception within 28 days after vaccination with MVA-BN-Filo or within 3 months after vaccination with Ad26.ZEBOV, will also be approached to consent for enrollment of their offspring into the roll-over study, according to the same rules that apply for the other subjects. Subjects in France who agree to continue the long-term follow-up after Day 365 and reach the Day 365 visit before the roll-over study is opened, will have further follow-ups in the current study until they have started in the roll-over study or for an additional 12 months (whichever comes first) or discontinued earlier. These subjects will be contacted by telephone every 3 months after Day 365 (subjects will only visit the site when clinically indicated) for the collection of information on adverse events, serious adverse events, and immediate reportable events (IREs) that were ongoing at the Day 365 visit, and to report and follow up on new serious adverse events, pregnancies, and IREs.

SUBJECT POPULATION

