Interim analyses may be performed during the study for regulatory purposes or for the purpose of informing future vaccine-related decisions in a timely manner. The primary analysis will be performed when all subjects have completed the 6-month post-boost visit or discontinued earlier and the clinical database is locked. This analysis will include 6-month post-boost safety and all available immunogenicity data up to this point. The final analysis will be performed when all subjects have completed the last study-related visit or discontinued earlier. Specific details will be provided in the SAP.

An IDMC will be established to monitor data on a regular basis to ensure the continuing safety of the subjects enrolled in the study.

Safety Analyses

No formal statistical testing of safety data is planned. Safety data will be analyzed descriptively (including 95% confidence intervals, if applicable), by cohort and overall. For each adverse event, the number and percentage of subjects who experience at least 1 occurrence of the given event will be summarized by group. Summaries, listings, datasets, or subject narratives may be provided, as appropriate, for those subjects who die, who discontinue study vaccine due to an adverse event, or who experience a severe or a serious adverse event. The most severe laboratory abnormalities following vaccination will be tabulated. Abnormalities in vital signs, ECG parameters, and physical examination following vaccination will be tabulated by most severe abnormality grade.

Immunogenicity Analyses

Descriptive statistics (actual values and changes from baseline, including 95% confidence intervals, if applicable) will be calculated for continuous immunologic parameters at each time point analyzed. Graphical representations of changes in immunologic parameters will be prepared, as applicable. Frequency tabulations will be calculated for discrete (qualitative) immunologic parameters at each time point analyzed. In addition, differences between the vaccination schedules will be evaluated at the 21-day post-boost, 6-month post-boost and Day 365 visits.

TIME AND EVENTS SCHEDULE

Cohorts I, II and III	Screening Phase ^a (≤12 weeks)	Vaccination and Post-vaccination Phase ^{b,c}									Long-term Follow-up Phase ^{c,d}	
		Day 1	Day 4	Day 8	-	Day 29	Day 32	Day 36	Day 50	Day 71 ^b	Day 209	Day 365 ^e
					-	Day 57	Day 60	Day 64	Day 78	Day 99 ^b	Day 237	
Group 1	Group 2	Group 3	Day 15 ^f	Day 85	Day 88	Day 92	Day 106	Day 127 ^b	Day 265			

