While replicating smallpox vaccines have been associated with an increased risk to develop myo/pericarditis,²¹ this has not been observed with MVA-BN and is not expected with this highly attenuated, non-replicating vaccine. Based on observations with first- and second-generation replication-competent smallpox vaccines, particular attention has been placed on the monitoring for cardiac signs and symptoms in all clinical studies using MVA-BN. Despite the close cardiac monitoring, no event indicating a case of pericarditis has been observed in any completed MVA-BN study. There has been 1 case of chest pain that might be indicative of pericarditis (consisting of chest pain only with no other cardiac findings suggestive of pericarditis) with previous MVA use although this diagnosis was not finally confirmed and the subject fully recovered. In a review of prospective surveillances for cardiac adverse events in 6 different clinical studies in 382 subjects receiving MVA vaccines, only 1 (0.3%) subject met the criteria for vaccine-induced myocarditis and eventually the subject was found to suffer from exercise-induced palpitations. Self-limited mild elevations in troponin I were recorded in 3 (0.8%) subjects without evidence of myo/pericarditis.⁷ Based on the current exposure data in more than 8,100 subjects vaccinated with MVA-BN and other MVA-BN recombinant products, the safety profile of MVA-BN has shown to be comparable with other licensed, live attenuated vaccines.

Pregnancy and Birth Control

The effect of the study vaccines on a fetus or nursing baby is unknown, as well as the effect on semen, so women of childbearing potential, and men having sexual intercourse with women, are required to agree to practice adequate birth control measures for sexual intercourse from at least 28 days before the prime vaccination (or prior to enrollment for men) until at least 3 months after the prime vaccination or up to 1 month after the boost vaccination (whichever takes longer), see Sections 4.1 and 4.3. Women who are pregnant or breast-feeding, or are planning to become pregnant while enrolled in the study until at least 3 months after the prime vaccination or up to 1 month after the boost vaccination (whichever takes longer) will be excluded from enrollment into the study.

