
A placebo control will be used (in Cohorts II and III) to establish the frequency and magnitude of changes in clinical and immunologic endpoints that may occur in the absence of Ad26.ZEBOV and MVA-BN-Filo. Blind treatment will be used to reduce potential bias during data collection and evaluation of clinical safety endpoints. Blinding will be guaranteed by the preparation of study vaccine by unblinded qualified study-site personnel not involved in any other study-related procedure and by the administration of vaccine in a masked syringe by a study vaccine administrator (see [Definitions of Terms](#)).

The rationale for defining the study as an observer-blind study is that the subjects and study-site personnel will not be blinded to the vaccination schedule and no additional placebo injections will be administered to mask the regimens across groups; blinding will only mask the administration (and observations) of Ad26.ZEBOV, MVA-BN-Filo or placebo within groups.

Study Groups

The 3 vaccination schedules (Groups 1, 2, and 3) will only differ in the timing of the boost vaccination (ie, 28-, 56- or 84-day interval), while the dose of each vaccine and the sequence of vaccination will be identical. The prime vaccine consists of Ad26.ZEBOV at a dose of 5×10^{10} vp and the boost vaccine consists of MVA-BN-Filo at a dose of 1×10^8 Inf.U (nominal titer), which corresponds to the dose of 1×10^8 TCID₅₀ that is used in the current Phase 1 studies. The safety, tolerability and immunogenicity results for the 3 vaccination schedules will be evaluated in the study.

DNA Collection

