9.1.4. Post-vaccination Phase

The subjects will come to the site at 3 and 7 days after each vaccination and also at 21 and 42 days after the boost vaccination as indicated in the [Time and Events Schedule](#). In Cohorts I and II, the subjects will come to the site for additional post-vaccination visits as indicated in the [Additional Time and Events Schedule](#). The 42-days post-boost visit (Cohorts I and II) may be replaced by a telephone call if the subject is not able to come to the site.

The subject's diary will be reviewed by study-site personnel at 3 and 7 days after each vaccination. The investigator will examine the injection site for occurrences of erythema, induration/swelling, and pain/tenderness, and will ask if itching at the injection site occurred at these visits in order to complete the relevant parts of the CRF.

Blood sampling for hematology and chemistry (fasting or non-fasting) at 7 days after each vaccination and an abbreviated, symptom-directed physical examination (as indicated by the investigator) will be performed. An ECG will be recorded at 7 days after the boost vaccination. Adverse events, serious adverse events and pregnancies will be collected and documented on the CRF, together with the information on any concomitant therapies. For reporting of IREs, refer to Section 12.3.3.

Blood samples for core immunogenicity assessments in Cohorts II and III will be collected as indicated in the [Time and Events Schedule](#) and Section 9.3.2. Blood samples for additional immunogenicity assessments in Cohort II and for specific immunogenicity assessments in Cohort I will be collected as indicated in the [Additional Time and Events Schedule](#) and Section 9.3.2.

Subjects will be instructed to contact the investigator before the next visit (ie, 6 months post-boost) if they experience any adverse event or intercurrent illness that they perceive as relevant and/or can be possibly related to study vaccine in their opinion.

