11.4. Safety Analyses

No formal statistical testing of safety data is planned. Safety data will be analyzed descriptively (including 95% confidence intervals, if applicable), by cohort and overall.

Baseline for all safety parameters will be defined as the last value before the prime vaccination.

Adverse Events (Including Reactogenicity)

The verbatim terms used in the CRF by investigators to report adverse events will be coded using the Medical Dictionary for Regulatory Activities (MedDRA). All reported adverse events (solicited local, solicited systemic, and unsolicited) will be included in the analysis. For each

adverse event, the number and percentage of subjects who experience at least 1 occurrence of the given event will be summarized by group. Summaries, listings, datasets, or subject narratives may be provided, as appropriate, for those subjects who die, who discontinue study vaccine due to an adverse event, or who experience a severe or a serious adverse event.

The analysis for solicited adverse events will be done on those subjects in the Full Analysis set for whom reactogenicity assessments are available in the database. The analysis of unsolicited adverse events will be done on the Full Analysis set.

Clinical Laboratory Tests

Laboratory abnormalities will be determined according to the toxicity grading tables, and in accordance with the normal ranges of the clinical laboratory. The most severe laboratory abnormalities following vaccination will be tabulated per regimen.

Vital Signs and Electrocardiogram

Vital signs and ECG abnormalities following vaccination will be tabulated by most severe abnormality grade.

Physical Examination

Physical examination abnormalities following vaccination will be tabulated by most severe abnormality grade.

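### SAP 7.4 replaces the protocol's graded ECG tabulation with a listing, without declaring the change, so no planned output gives ECG abnormality rates by grade for active vaccine and placebo

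*SAP*

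**What the plan says.** Protocol 11.4 states: "Vital signs and ECG abnormalities following vaccination will be tabulated by most severe abnormality grade". The synopsis says the same: "Abnormalities in vital signs, ECG parameters, and physical examination following vaccination will be tabulated by most severe abnormality grade".

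SAP 7.4 describes the schedule: "a single, 12-lead ECG was performed at screening, pre-boost and 7 days post-boost, and interpreted locally". It then notes that further ECGs could be taken if signs or symptoms called for them, and concludes that "only a listing of subjects with an electrocardiogram abnormality following vaccination will be generated". No table follows. The section neither cites the ECG grades in SAP Attachment 3 nor defines what counts as an abnormality.

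SAP section 3, on changes to the planned analysis, has two entries. Both concern the immunogenicity and per protocol analysis sets.

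**The concern.** The SAP drops an analysis that the protocol specifies, and the reason it gives does not lead to that result. ECGs taken only on clinical indication are a selected sample, and a rate based on them would mislead. The pre-boost and 7-day post-boost ECGs are fixed visits for every boosted subject in both arms, and for them a rate is meaningful.

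A listing shows who had an abnormality. It does not show how many subjects were assessed, how abnormalities divide by grade, or how active compares with placebo. The protocol (3.2) says the placebo control is there "to establish the frequency and magnitude of changes in clinical and immunologic endpoints" that may arise without the vaccines. Cardiac safety is also a topic the protocol raises itself: section 1.2.4 says that "particular attention has been placed on the monitoring for cardiac signs and symptoms in all clinical studies using MVA-BN".

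**Working it through.** No figure in the plan needs reproducing. The check is mainly a comparison of text, followed by arithmetic on how informative the missing table would be.

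**1. Is the post-vaccination ECG scheduled?** Yes. Protocol 9.1.4: "An ECG will be recorded at 7 days after the boost vaccination". Protocol 9.1.3 requires an ECG before the boost, which is already after the prime. The Time and Events Schedule marks both visits. Subjects boosted late are covered too, because the synopsis says: "Vaccinated subjects have been following the same post-boost vaccination schedule as those subjects unaffected by the pause".

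**2. Does the SAP's reason apply to these ECGs?** No. It describes unscheduled ECGs only. SAP 7.3 gives different reasons for listing vital signs (measured only at screening and before each vaccination) and physical examination (symptom-directed after screening). Those are not at issue here.

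**3. How does the SAP treat similar data?** Haematology and chemistry are also drawn before the boost and 7 days after it. SAP 7.2.3 gives them number and percentage of worst abnormality by regimen and period, and again pooled by vaccine.

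**4. Are grades available?** Yes. SAP Attachment 3 has Grades 1 to 3 for QTc and PR interval. The QTc rows need repair before use:
- An increase of exactly 60 ms meets both Grade 2 (30-60 ms) and Grade 3 (60 ms or more).
- Grade 1 includes any increase below 30 ms, so trivial changes would count as abnormal.

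**5. How precise would the table be?** Inputs come from the cohort table in protocol 3.1.
- Active, Cohorts II and III: 3 × (84 + 80) = 492.
- Placebo, Cohorts II and III: 3 × (6 + 24) = 90.
- Check: 492 + 90 + 30 (open-label Cohort I) = 612, the planned total.

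The documents do not give the number boosted by arm. SAP 1.4 reports about 423 subjects in all, and 423/612 = 69%. I therefore show 100%, 70% and 50% of planned numbers as assumptions. With zero events the upper limit is 1 − 0.025^(1/n). The intervals are exact (Clopper-Pearson) around an illustrative rate near 5%, rounded to whole subjects.

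| Share with the ECG | Active n | Placebo n | Upper limit at 0 events, active / placebo | 95% CI near 5%, active | 95% CI near 5%, placebo |
|---|---|---|---|---|---|
| 100% | 492 | 90 | 0.7% / 4.0% | 3.3-7.4% | 1.2-11.0% |
| 70% | 344 | 63 | 1.1% / 5.7% | 2.9-7.8% | 1.0-13.3% |
| 50% | 246 | 45 | 1.5% / 7.9% | 2.5-8.4% | 0.5-15.1% |

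Within one schedule the planned placebo number is 6 + 24 = 30, and zero events would leave an upper limit of 1 − 0.025^(1/30) = 11.6%. The table is feasible and informative for active vaccine, but imprecise for placebo.

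**The case against.** A reader might infer that ECG abnormalities cannot be compared with placebo at all. The documents do not support that.

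- Protocol 9.2.2 requires clinically significant ECG abnormalities up to 42 days post-boost to be recorded as adverse events. SAP 7.1.3 gives unsolicited events with number and percentage by system organ class and preferred term, by schedule, with similar tables pooled by vaccine. The 7-day ECG falls well inside the Post-dose 2 period, which runs to relative Day 29.
- SAP 5.1 tabulates how many subjects entered each analysis period, and subjects without Dose 2 have no Post-dose 2 period. The number due a 7-day ECG can therefore be approximated. Only missed ECGs are unaccounted for.

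A reader might also infer that the 7-day ECG was put in place to detect myo/pericarditis. No passage says so. Protocol 1.2.4 states that the condition has not been observed with MVA-BN and is not expected. Cardiac signs or symptoms after the boost have their own work-up in 9.2.2. The ECG grades in Attachment 3 cover arrhythmia, QTc and PR, so a worst-grade table would mostly show interval changes.

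Finally, ECG is not a primary endpoint, and safety is descriptive with no formal testing.

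All of this stands, and it limits the point without removing it. The adverse event route depends on the investigator's judgement of a locally read tracing and leaves out graded changes not judged significant. The number entering a period is not the number with an ECG. None of it explains why the protocol's table was dropped or why section 3 does not mention it.

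**Conclusion.** The point holds in a limited form. SAP 7.4 departs from protocol 11.4 and the synopsis for a reason that does not cover the scheduled ECGs, and the departure is not declared. No planned output gives graded ECG abnormality rates by active vaccine and placebo with the number assessed.

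The cost is one descriptive safety summary. The primary endpoints are untouched, clinically significant findings are still counted, and the placebo column would be imprecise even at full planned size. It is still worth correcting, because the data are already collected and the protocol promised the table.

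This rests on two assumptions. First, the France-specific version of Amendment 5, which the SAP cites but which I have not seen, carries the same ECG commitment. Second, the 50% to 100% range reasonably brackets the numbers with an ECG; 100% is shown for reference only, since enrolment stopped early.

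**What to change.** In SAP 7.4, add a descriptive table of number and percentage of subjects by worst post-baseline ECG abnormality grade:

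- **Rows:** the pre-boost ECG (after Dose 1) and the 7-day ECG (after Dose 2), shown separately. Define them by visit. Under SAP Table 2 the Post-dose 1 period ends at relative Day 29, so the pre-boost ECG in the 56- and 84-day schedules would otherwise fall into the follow-up phase.
- **Columns:** schedule, active versus placebo, for pooled Cohorts II and III, plus a column pooled across schedules as for laboratory data. Show Cohort I separately.
- **Denominator:** subjects with an ECG at that visit, with the number printed.
- **Baseline:** the last ECG before the prime, which is the screening ECG. This matches the baseline definition in protocol 11.4. The pre-boost ECG is already post-prime.
- **Grading:** cite Attachment 3, state which abnormality qualifies, and reconcile the QTc criteria first. Place a 60 ms increase in one grade only, and show the absolute-interval and change criteria separately so that increases below 30 ms do not swell Grade 1.
- **Listing:** keep it, including unscheduled ECGs.

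If the sponsor prefers the listing alone, section 3 should declare the change and give a reason that applies to the scheduled ECGs. That would settle the reporting gap but would not restore the rates.

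The cost is one more table from data in hand, with a placebo column that needs cautious reading.
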